12.1. DERIVATIONS

- Duration of antifungal medications (days) = stop date – start date + 1 for each antifungal therapy.

See [appendix 2](#) for handling of partial dates for medications. In Case of missing stop date, duration of antifungal derivation should be performed as follows:

- For Prior or concomitant medications, if stop date is missing, use main phase treatment end date as stop date . If the main phase treatment end date is missing then use last known alive date as stop date.

13. NON-MEDICATION PROCEDURES

Non-medication procedures will be presented for the ITT population by SOC and PT and coded using the most recent

Document: \\weedc-vnasc01\BIOSdata\F2G\F901318\ [Redacted]
Author: [Redacted] Version Number: 3.0
Version Date: 06Apr2023
Template No.: CS_TP_BS016 Revision 6 Reference: CS_WI_BS005
Effective Date: 02Dec2019

version of MedDRA.

See [appendix 2](#) for handling of partial dates for non-medication procedures. In the case where it is not possible to define a procedure as prior, concomitant or post, the procedure will be classified by the worst case; i.e. concomitant.

- 'Prior' non-medication procedures are procedures which were started prior to the first dose of study medication.
- 'Concomitant' non-medication procedures are procedures which were:

started prior to, on or after the first dose of study medication but prior to last dose of study medication,

AND ended on or after the date of first dose of study medication or were ongoing at the end of the study.

- 'Post' non-medication procedures are procedures which were started after the last dose of study medication.

14. STUDY MEDICATION EXPOSURE

Exposure to study medication in days will be presented for the SAF.

The date of first study medication administration will be taken from the start date and time of administration for dose number 1 on the Exposure eCRF page. The date of last study medication for the main study phase will be the stop date and time of administration for last dose on the Exposure eCRF page that is stopped prior to the main study phase end.. The date of last study medication for the extended treatment phase will be the stop date and time of administration for last dose on the Exposure eCRF page that is stopped prior to the extended treatment phase end..

Interruptions, compliance, and dose changes are not taken into account for duration of exposure.

A summary table for duration of exposure by baseline DRC Adjudicated category, overall, and dose type(overall, fixed dose, adjusted dose) will be presented.

Duration of Exposure will also be presented for the below categories:

For Main study phase:

- ≤ 42 days
- > 42 days to ≤ 84 days
- >84 days

Document:	\\weedc-vnasc01\BIOSdata\F2G\F901318\		
Author:		Version Number:	3.0
		Version Date:	06Apr2023
Template No.:	CS_TP_BS016 Revision 6	Reference:	CS_WI_BS005
Effective Date:	02Dec2019		

F2G Ltd.
PROTOCOL F901318/0032

For Extended treatment phase:

- ≤ 42 days
- > 42 days to ≤ 84 days
- > 84 days to ≤ 180 days
- > 180 days to ≤ 365 days
- > 365 days

Waterfall plot for duration of exposure by baseline DRC-adjudicated disease category, dose type and overall will be presented.

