8.2.4 Safety Endpoints

Descriptive statistics will be used to present the safety outcomes including:

- Changes in concurrent medication dose and/or frequency resulting from potential DDIs
- Hospitalisations
- Overall exposure, individual dose modification, dose intensity.
- Incidence of treatment-emergent and other (including but not limited to):
 - AEs
 - SAEs (including deaths)
 - AEs leading to death
 - Liver-related AEs
 - AEs leading to premature treatment discontinuation
 - AEs leading to premature study withdrawal
 - AEs by relationship

- AEs by severity (CTCAE grade)
- AESIs
- Change from baseline in clinical laboratory test results and incidence of pre-defined treatment-emergent abnormalities (CTCAE)
- Liver-related toxicity: Incidence and time-to-event analyses of elevations in ALT, AST, bilirubin, as described in detail in Section 6.4.2.3.
- Change from baseline in ECG results and incidence of pre-defined treatment-emergent abnormalities (CTCAE)
- Change from baseline in vital signs (including weight and BMI) and incidence of pre-defined treatment-emergent abnormalities (CTCAE)
- [REDACTED]
- Physical examination: Any abnormal clinically significant findings, as judged by the Investigator, will be listed in a by-patient data listing only.

A treatment-emergent AE (TEAE) is defined as any AE starting or worsening on or after the first dose of study drug up to and including last dose of study drug or during the post-treatment FU. Treatment-emergent AEs which occur in the main study phase or FU will be presented in the study report; TEAEs which occur in the ET phase or post-ET FU will be presented in the report addendum.

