8.9.1 Exposure

Overall exposure will be summarised by taking individual dose modification and dose intensity into account.

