14.1. DERIVATIONS

Duration of exposure (days) up to end of main study phase = date of last study medication administration for the main study phase – date of first study medication administration + 1.

Duration of exposure (days) up to end of extended treatment phase = date of last study medication administration for the extended treatment phase – date of first study medication administration + 1.

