15. MAIN STUDY MEDICATION COMPLIANCE

Overall compliance to main study medication will be presented in the form of listing for the SAF.

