15.1. DERIVATIONS

Overall compliance to main study medication—based on the drug accountability and exposure data—will be calculated as the actual number of tablets taken (prescribed number of tablets as recorded on exposure eCRF – total number of missed tablets) divided by the prescribed number of tablets expressed as a percentage.

Up to and including protocol amendment 4 patients will receive a loading regimen of approximately 4 mg/kg of F901318 divided into two or three doses (12 or 8 hours apart respectively), followed by a maintenance regimen of approximately 2.5 mg/kg/day divided into two or three doses from Day 2 onwards. Based upon emerging data from studies in healthy volunteers, the recommended dose regimen may be revised to total daily dosages of up to 300 mg

Document: \\weedc-vnasc01\BIOSdata\F2G\F901318\ [Redacted]
Author: [Redacted] Version Number: 3.0
Version Date: 06Apr2023
Template No.: CS_TP_BS016 Revision 6 Reference: CS_WI_BS005
Effective Date: 02Dec2019

divided into two or three doses.

From protocol amendment 6 onwards patients will receive a one-day oral loading dose of 150 mg bid (dosed 12 ± 1 hours apart) followed by a maintenance dose regimen of 90 mg bid (dosed 12 ± 1 hours apart) from Day 2 onwards. Based upon clinical evaluation of efficacy by the Investigator, stepwise increases of maintenance doses of F901318 (to 120 mg bid, then 150 mg bid) may be permitted, following discussion with the MM.

Due to the dose changing nature of this study, prescribed number of tablets will be calculated from the Exposure eCRF page as follows:

$[(\text{Dose number 1's End date and time of study medication administration} - \text{Dose number 1's Start date and time of study medication administration} + 1) \times \text{Dose number 1's Total Daily Dose}] + [(\text{Dose number 2's End date and time of study medication administration} - \text{Dose number 2's Start date and time of study medication administration} + 1) \times \text{Dose number 2's Total Daily Dose}]$

+ ... +

$[(\text{Dose number n's End date and time of study medication administration} - \text{Dose number n's Start date and time of study medication administration} + 1) \times \text{Dose number n's Total Daily Dose}]$,

where n is the largest dose number recorded on the Exposure eCRF page with End date of study medication administration equal to the date of last study medication for the main study phase. <<divide by 30 (30mg per tablet)>>

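### The legible SAP has no summary of dose modification or dose intensity, which the protocol names as a safety endpoint, and its elapsed-day duration counts drug-free gaps as exposure

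*SAP*

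**What the plan says.** The protocol lists this safety endpoint in the Synopsis and in 8.2.4: "Overall exposure, individual dose modification, dose intensity". Section 8.9.1 turns it into an analysis commitment: "Overall exposure will be summarised by taking individual dose modification and dose intensity into account".

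SAP 14 opens with "Exposure to study medication in days will be presented for the SAF". It then sets the rule "Interruptions, compliance, and dose changes are not taken into account for duration of exposure". SAP 14.1 defines main-phase duration as "date of last study medication administration for the main study phase – date of first study medication administration + 1". A second formula, labelled "Duration of exposure (days) up to end of extended treatment phase", also subtracts the date of the first study dose. SAP 14 breaks duration down by disease category and by dose type (fixed or adjusted). It also gives banded categories for each phase; the ET bands begin at 42 days or less, then over 42 to 84 days.

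Dose records are used in the compliance derivation of SAP 15.1: "Due to the dose changing nature of this study, prescribed number of tablets will be calculated from the Exposure eCRF page as follows". The output is limited, however: "Overall compliance to main study medication will be presented in the form of listing for the SAF".

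SAP 3.3, which lists departures from the protocol, does not mention exposure in its legible text.

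**The concern.** A named safety endpoint has no planned summary. Under Protocol 5.1 the dose may be adjusted for liver tests or interacting drugs, or raised in steps when response is judged inadequate, and dosing may be interrupted. Evaluating dose adaptation is an exploratory objective (Protocol 3.3, SAP 2.3). SAP 18.1.6 also plans a histogram of certain events, whose type is redacted, by weeks of treatment. A reader of the safety results needs to know how many days patients took drug and how much they took. Elapsed days answer neither question for a patient whose dosing was interrupted, and they do not give the amount for anyone whose dose was changed.

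**Working it through.** The documents give no exposure figure to reproduce, so the check applies the SAP 14.1 formula to example courses.

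**Inputs from the documents.** Loading is 150 mg twice daily for one day (300 mg/day), then 90 mg twice daily (180 mg/day). Permitted increases are to 120 mg and then 150 mg twice daily (240 and 300 mg/day). Tablets are 30 mg. After a gap of more than 48 hours, dosing restarts with a loading regimen (Protocol 5.1). A patient with a successful outcome at end of treatment who restarts before the 28-day follow-up visit is treated as interrupted (Protocol 5.1), which allows a gap of up to about 27 days in that subset.

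**Assumptions, for arithmetic only.** The course runs from Day 1 to Day 84. Gaps start on Day 29. The timing of dose changes and the size of the reduction (a halving) are assumed; the documents state no reduction size.

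**Formulas.** SAP duration = last date − first date + 1 = 84 − 1 + 1 = 84 in every row. Days dosed = 84 − g for a gap of g days. Overstatement of days = 84/(84 − g) − 1. Cumulative mg = sum of days × mg/day over dose records. Relative amount = cumulative mg ÷ mg for the unmodified course, which is 300 + 83 × 180 = 15,240 mg.

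| Course | SAP days | Days dosed | Days overstated | mg received | Relative amount |
|---|---|---|---|---|---|
| Unmodified | 84 | 84 | 0% | 15,240 | 100% |
| 7-day gap | 84 | 77 | 84/77: +9.1% | 14,100 | 92.5% |
| 14-day gap | 84 | 70 | 84/70: +20.0% | 12,840 | 84.3% |
| 27-day gap | 84 | 57 | 84/57: +47.4% | 10,500 | 68.9% |
| Raised to 240 mg/day on Day 15, 300 mg/day on Day 29 | 84 | 84 | 0% | 22,800 | 149.6% |
| Halved to 90 mg/day from Day 15 (assumed) | 84 | 84 | 0% | 8,940 | 58.7% |
| 7-day gap, then 300 mg/day | 84 | 77 | +9.1% | 19,860 | 130.3% |

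Example sums: the 7-day gap gives 300 + 27 × 180 + 300 + 48 × 180 = 14,100 mg. The escalated course gives 300 + 13 × 180 + 14 × 240 + 56 × 300 = 22,800 mg.

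All seven courses are reported as 84 days. The last row overstates days while the patient receives more drug than in the unmodified course.

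**Does compliance fill the gap?** If the interruption is recorded as separate dose records, SAP 15.1 gives 14,100/30 = 470 prescribed tablets for the 7-day-gap patient, against 15,240/30 = 508 without a gap. With no tablets entered as missed, compliance = (470 − 0)/470 = 100%. The gap has left the denominator.

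**ET categories.** ET entry requires 84 to 90 completed days of main-phase treatment (Protocol 4.3.1.1). The only ET formula counts from the first main-phase dose (SAP 14 and 14.1). With one ET day, the shortest possible value is 84 + 1 = 85. The bands up to 42 days and over 42 to 84 days are therefore empty if this formula fills them.

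**The case against.** The best reply is that the SAP is open about what it reports. The quoted rule is limited to duration, exposure is labelled in days, and the study is descriptive. Dose changes and interruptions also appear elsewhere. Events leading to a dose increase or reduction are tabulated (SAP 18.1.8). AESIs leading to temporary discontinuation are tabulated and the duration of discontinuation is listed (18.1.6). Total daily dose is plotted by subject with trough levels (17.1), and PK is summarised by interacting-drug group (17.1.1). Compliance is listed (15).

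Much of this stands, and it rules out four stronger readings that a reader might infer:

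- *Reported exposure overstates drug received.* The SAP reports no amount of drug. The only dose changes whose size the documents state are upward, and there elapsed days would understate intake.
- *Dose changes and interruptions would be invisible.* The outputs above show some of them.
- *Any stop of up to four weeks counts as an interruption.* That provision covers only patients with a successful outcome who need retreatment, after consulting the Medical Monitor. Protocol 5.1 otherwise says interruptions should be avoided.
- *ET exposure is overstated by 84 to 90 days.* The formula's label describes a cumulative duration and is accurate as such. The defect is the mismatch with the bands, which make sense only as ET-only time.

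The reply does not close the main gap. The adverse-event tables miss changes made for efficacy or for interactions without an event. Listings and individual plots do not amount to the summary that 8.9.1 promises.

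Two limits apply. SAP 3.3 is partly redacted, and the output templates mentioned in SAP 8 were not available, so an entry there cannot be excluded. Dose intensity also needs a reference dose, which is not obvious for patients treated under the earlier mg/kg scheme (SAP 3.1) or given individual adjustments.

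**Conclusion.** The omission holds for the legible text: a protocol safety endpoint and its analysis commitment have no aggregate summary in the SAP, and no departure is declared. For interrupted patients in an 84-day course, elapsed duration overstates days on drug by about 9% (7-day gap) to 47% (27-day gap, close to the longest that the retreatment provision allows). These are per-patient illustrations, not expected averages, because the documents give no frequency of gaps. For amount received, the direction is not fixed: the example courses with a dose change and no gap run from about 59% to 150% of the unmodified amount, all reported as 84 days. The ET point is an internal inconsistency between bands and formula; it assumes that the only ET formula given is the one used to fill the bands. None of this touches the primary efficacy result. It should be corrected, because it bears on how the safety and dose-adaptation results are read.

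**What to change.** 1. Keep elapsed duration, labelled as first-to-last-dose time.
2. Add, on the safety set and by dosing type, from the Exposure eCRF: days actually dosed (excluding interruptions), cumulative dose in mg, mean daily dose, and counts of interruptions, reductions and increases.
3. Give dose intensity against a stated reference, for example the patient's own assigned starting regimen.
4. Compute the ET bands from the first ET dose, and label the existing formula as cumulative main-phase plus ET duration.
5. If the sponsor prefers not to produce the summary, declare and justify the omission in SAP 3.3.

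The cost is modest. SAP 15.1 already sums days × total daily dose over dose records before dividing by 30, so cumulative mg is an intermediate result of a planned derivation. The rest is a small amount of programming, plus the decision on a reference regimen for patients dosed under the earlier mg/kg scheme.

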14.1. DERIVATIONS

Duration of exposure (days) up to end of main study phase = date of last study medication administration for the main study phase – date of first study medication administration + 1.

Duration of exposure (days) up to end of extended treatment phase = date of last study medication administration for the extended treatment phase – date of first study medication administration + 1.

15. MAIN STUDY MEDICATION COMPLIANCE

Overall compliance to main study medication will be presented in the form of listing for the SAF.

15.1. DERIVATIONS

Overall compliance to main study medication—based on the drug accountability and exposure data—will be calculated as the actual number of tablets taken (prescribed number of tablets as recorded on exposure eCRF – total number of missed tablets) divided by the prescribed number of tablets expressed as a percentage.

Up to and including protocol amendment 4 patients will receive a loading regimen of approximately 4 mg/kg of F901318 divided into two or three doses (12 or 8 hours apart respectively), followed by a maintenance regimen of approximately 2.5 mg/kg/day divided into two or three doses from Day 2 onwards. Based upon emerging data from studies in healthy volunteers, the recommended dose regimen may be revised to total daily dosages of up to 300 mg

Document: \\weedc-vnasc01\BIOSdata\F2G\F901318\ [Redacted]
Author: [Redacted] Version Number: 3.0
Version Date: 06Apr2023
Template No.: CS_TP_BS016 Revision 6 Reference: CS_WI_BS005
Effective Date: 02Dec2019

divided into two or three doses.

From protocol amendment 6 onwards patients will receive a one-day oral loading dose of 150 mg bid (dosed 12 ± 1 hours apart) followed by a maintenance dose regimen of 90 mg bid (dosed 12 ± 1 hours apart) from Day 2 onwards. Based upon clinical evaluation of efficacy by the Investigator, stepwise increases of maintenance doses of F901318 (to 120 mg bid, then 150 mg bid) may be permitted, following discussion with the MM.

Due to the dose changing nature of this study, prescribed number of tablets will be calculated from the Exposure eCRF page as follows:

$[(\text{Dose number 1's End date and time of study medication administration} - \text{Dose number 1's Start date and time of study medication administration} + 1) \times \text{Dose number 1's Total Daily Dose}] + [(\text{Dose number 2's End date and time of study medication administration} - \text{Dose number 2's Start date and time of study medication administration} + 1) \times \text{Dose number 2's Total Daily Dose}]$

+ ... +

$[(\text{Dose number n's End date and time of study medication administration} - \text{Dose number n's Start date and time of study medication administration} + 1) \times \text{Dose number n's Total Daily Dose}]$,

where n is the largest dose number recorded on the Exposure eCRF page with End date of study medication administration equal to the date of last study medication for the main study phase. <<divide by 30 (30mg per tablet)>>

Total number of missed tablets will be calculated as follows:

Sum of number of tablets missed, as entered on the Drug Accountability eCRF page for the main study phase.

Overall compliance to main study medication will be calculated as follows:

$$\frac{\text{Prescribed number of tablets} - \text{Total number of missed tablets}}{\text{Prescribed number of tablets}} \times 100$$

16. EFFICACY OUTCOMES

For each efficacy variable, descriptive statistics summarising the data overall and by Baseline DRC-adjudicated disease category will be presented. Additional statistical analyses for the efficacy variables including the subgroup analyses are described below. A list of the subgroups assessed is given in [section 7.4](#).

Document: \\ieedc-vnasc01\BIOSdata\F2G\F901318\ [Redacted]
Author: [Redacted] Version Number: 3.0
Version Date: 06Apr2023
Template No.: CS_TP_BS016 Revision 6 Reference: CS_WI_BS005
Effective Date: 02Dec2019

F2G Ltd.
PROTOCOL F901318/0032

16.1. PRIMARY EFFICACY

16.1.1. PRIMARY EFFICACY VARIABLE & DERIVATIONS

The primary efficacy variable is the DRC-adjudicated overall response at Day 42, as determined by an independent DRC using a combination of clinical, mycological and radiological results, and collected in a separate DRC adjudicated outcome database.

Table A presents the criteria for invasive fungal disease assessment of overall response.

Table A: Criteria for IFD assessment of overall response

Overall Response	Criteria
Success-Complete*:	
 Clinical: Meets Criteria for Resolution Complete; Radiological (if assessed): Shows resolution of radiological abnormalities ($\geq 90\%$ response); Mycological: Meets criteria for presumed or documented eradication.
Success-Partial*:	
 Clinical: Meets Criteria for Resolution-Complete or Resolution-Partial; Radiological: Shows resolution or improvement of radiological abnormalities (at least 25% response); Mycological: Meets criteria for presumed or documented eradication.
Failure-Stable:	
 Clinical: No improvement and no worsening of any attributable clinical symptoms and physical findings previously noted and no new attributable clinical symptoms or physical findings of IFD (Failure-Stable); 
OR
 
 Radiological (if assessed): Shows no evidence of progression OR $< 25\%$ improvement of radiological abnormalities; 
OR
 
 Mycological: Had mycological evidence at baseline AND does not meet criteria for presumed or documented eradication.
Failure-Progression:	
 Clinical: Either worsening of attributable clinical symptoms or physical findings of IFD or appearance of new attributable symptoms or findings of IFD (Failure-Progression); 
OR
 
 Radiological: Worsening or new radiological abnormalities; 
OR
 
 Mycological: Has mycological evidence for a recurrent or emergent IFD, OR alternative systemic antifungal treatment required.

Document: \\weedc-vnasc01\BIOSdata\F2G\F901318\

Author:

Version Number:

3.0

Version Date:

06Apr2023

Template No.: CS_TP_BS016 Revision 6

Reference: CS_WI_BS005

Effective Date: 02Dec2019

F2G Ltd.
PROTOCOL F901318/0032

*For these categories, the only required data are the clinical and mycological data. The absence of radiological evaluations at a given time point does not prevent assignment to Success-Complete or Success-Partial. The rules defining success are tested in sequence with Success-Complete assigned if its rules are met and Success-Partial otherwise assigned. The rules for Failure are tested next and Failure is assigned if any of its rules are met. The rules for Stable are tested last.

Number and % of patients will be summarised for the 4 categories shown in Table A. N and % will also be summarised for the 3 categories of Success (Success-Complete, Success-Partial), Stable disease (Failure-Stable) and Failure (Failure-Progression, Death, and those patients for whom data at Day 42 cannot be collected or who are considered not evaluable at Day 42).

For statistical primary analysis of overall response rate, values will be assigned to the DRC-adjudicated overall response as follows:

- Success (Success-Complete, Success-Partial),
- Failure (Failure-Stable, Failure-Progression, Death, and those patients for whom data at Day 42 cannot be collected or who are considered not evaluable at Day 42). Patients withdrawn from study medication due to an unsuccessful overall outcome are required per protocol to return for the main study phase EOT visit but will not be asked to return for the Day 42 and/or Day 84 visits; these patients will be considered as failures at all subsequent timepoints.

As a key important analysis, patients with a stable disease outcome will be considered a success, i.e. assigning the DRC adjudicated response to categories as follows.

- Success (Success-Complete, Success-Partial, Failure-Stable)
- Failure (Failure-Progression, Death, and those patients for whom data at Day 42 cannot be collected or who are considered not evaluable at Day 42)

This alternative classification, where stable disease outcome can be considered a successful response in the timeframe of this evaluation, is an important analysis due to the nature of this challenging patient population for whom other therapies have already failed.

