6.3.1.1 Clinical Response

Clinical response will be based on clinical signs, physical findings, and symptoms relevant to each patient. The Investigator will be responsible for identifying and assessing clinical signs, physical findings, and symptoms related to the IFD reported for each patient. Assessment of clinical response will be based on changes from baseline signs, findings, and symptoms. Clinical signs, physical findings, and symptoms will be assessed [REDACTED]

[REDACTED] as shown in Table 1. Assessment at Day 42 and at Day 84 is required for all patients, including those who completed treatment before these visits.

For patients who receive ET with F901318, the Investigator's assessment of clinical response will be recorded at each visit to support continued treatment.

Baseline symptoms may need to include symptoms present at the time of the initial diagnosis of the qualifying infection. This situation may arise when a patient has had a prior therapy, responded to that therapy, but then developed intolerance to the therapy and is hence started on F901318 therapy without active symptoms at the point of study enrolment. Such prior symptoms will be recorded in the appropriate section of the eCRF.

The results of assessments of clinical signs, physical findings, and symptoms (including those performed outside of these mandatory scheduled timepoints) will be recorded in the eCRF.

An assessment of the patient's clinical response (all non-radiological clinical signs, physical findings, and symptoms related to IFD) will be recorded [REDACTED]

(Note that for patients planning to receive ET beyond Day 90, the Day 84 visit and the main study phase EOT visit will be combined into a single Day 84/EOS/EOT visit on approximately Day 90.)

- **Resolution-Complete:**

For patients with attributable clinical symptoms and physical findings of IFD present at baseline, Resolution-Complete is assigned if

- a) there is resolution of all attributable clinical symptoms and physical findings of IFD present at baseline or that appeared at a subsequent prior visit

AND

- b) no new clinical symptoms and physical findings of IFD are noted at the current visit.

For patients lacking attributable clinical symptoms and physical findings of IFD present at baseline*, Resolution-Complete is assigned if

- a) there is resolution of all attributable clinical symptoms and physical findings that appeared at a subsequent prior post-baseline visit

AND

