For statistical analysis of clinical response rate, values will be assigned to the DRC-adjudicated and Investigator-assessed clinical response as follows:

- Success (Resolution-Complete, Resolution-Partial),
- Failure (Failure-Stable, Failure-Progression, Deaths, and those patients for whom data at the specific visit cannot be collected or who are considered not evaluable at the specific visit).

Similarly to primary analysis, patients with a stable disease outcome will be considered a success, i.e. assigning the DRC adjudicated response to categories as follows.

- Success (Resolution-Complete, Resolution-Partial, Failure-Stable)
- Failure (Failure-Progression, Death, and those patients for whom data at the specific visit cannot be collected)

Document: \\weedc-vnasc01\BIOSdata\F2G\F901318\ [Redacted]
 Author: [Redacted] Version Number: 3.0
 Version Date: 06Apr2023
 Template No.: CS_TP_BS016 Revision 6 Reference: CS_WI_BS005
 Effective Date: 02Dec2019

or who are considered not evaluable at the specific visit)

Patients withdrawn from study medication due to an unsuccessful overall outcome are required per protocol to return for the main study phase EOT visit but will not be asked to return for the Day 42 and/or Day 84 visits; these patients will be considered as failures at all subsequent timepoints.

For the 4-week follow-up visit, only patients who did not enrol in the extension treatment phase will be considered.

16.1.5.4. DRC-adjudicated and Investigator-assessed radiological response at Day 7, Day 14, Day 28, Day 42, main study phase EOT, Day 84, and 4-week follow-up

DRC-adjudicated and Investigator-assessed radiological response at Day 7, Day 14, Day 28, Day 42, main study phase EOT, Day 84, and 4-week follow-up are secondary efficacy variables.

DRC-adjudicated radiological response is determined by an independent DRC and collected in a separate DRC adjudicated outcome database.

Investigator-assessed radiological response is collected on the Investigator's diagnostic and response assessment eCRF page.

For the 4-week follow-up visit, only patients who did not enrol in the extension treatment phase will be considered.

Table C presents the criteria for radiological response.

Table C: Criteria for radiological response

Radiology Response
≥ 90% improvement in aggregate (across all lesions if more than one lesion)
≥ 50 to < 90% improvement in aggregate (across all lesions if more than one lesion)

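### SAP Table A lets a patient meet Success-Partial and Failure-Progression at the same visit, and its footnote tests Success first, so a patient with a new lesion can be scored a Day 42 success

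*SAP*

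**What the plan says.** The primary variable in SAP 16.1.1 is overall response at Day 42, determined by the DRC from clinical, radiological and mycological components. The relevant parts of Table A and its footnote are:

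- **Success-Partial.** Clinical Resolution-Complete or Resolution-Partial, documented or presumed eradication, and on imaging: "Shows resolution or improvement of radiological abnormalities (at least 25% response".
- **Failure-Progression.** Three lines joined by OR. The radiological line is "Radiological: Worsening or new radiological abnormalities". The mycological line covers recurrent or emergent disease, and also the need for another systemic antifungal.
- **Order.** "The rules defining success are tested in sequence with Success-Complete assigned if its rules are met and Success-Partial otherwise assigned". Then "The rules for Failure are tested next and Failure is assigned if any of its rules are met". Finally, "The rules for Stable are tested last".

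Radiology is graded in SAP 16.1.5.4 (Table C) by net change, for example "≥ 50 to < 90% improvement in aggregate (across all lesions if more than one lesion". No level of that scale records a new lesion. Protocol 6.3.1.1 confines the clinical component to "all non-radiological clinical signs, physical findings, and symptoms related to IFD".

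Protocol Table 5 has essentially the same four rows. Its footnote places Success-Complete ahead of Success-Partial but sets no order between Success and Failure; the SAP adds that order.

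**The concern.** A sequence of rules is safe if the categories exclude one another, or if the disqualifying rule is read first. Here the categories overlap and the disqualifying rule is read second. A new radiological abnormality is one of the plan's own definitions of progression, yet a patient who has one can be counted among the responders.

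The rate affected is the primary result of an open-label single-arm study. SAP 16.1.3 sets it against an estimated historical rate, and Protocol 8.1 plans an initial analysis of 100 patients to consider whether approval might be possible. SAP 16.1.5.1 and 16.1.5.2 reuse Table A for the secondary DRC and investigator overall responses, and the stable-as-success analysis in 16.1.1 uses the same assigned categories.

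**Working it through.** The plan states no figure on this point, so there is none to reproduce. The check is whether the rows can overlap, by which routes, and what the footnote then does.

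**1. Does any component of Success-Partial block a new lesion?**

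| Component | Requirement | Excludes a new lesion? |
|---|---|---|
| Radiological | at least 25% aggregate improvement | No, it is a net figure |
| Clinical | complete or partial resolution, no new clinical findings | No, if the lesion is seen only on imaging |
| Mycological | documented or presumed eradication | No, it excludes new organisms only |

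Example with assumed sizes: baseline burden 100, old lesions shrink to 55, a new silent lesion of 10 appears. Aggregate improvement is (100 − 55 − 10)/100 = 35%, or (100 − 55)/100 = 45% if the new lesion is left out of the sum. Both exceed 25%. With Resolution-Partial and presumed eradication, the patient meets Success-Partial and also the radiological line of Failure-Progression.

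**2. Which routes overlap?** Take 5 clinical states, 5 imaged radiological levels with or without a new lesion plus not assessed (5 × 2 + 1 = 11), 6 mycological states, and another antifungal needed or not (2).

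- All combinations: 5 × 11 × 6 × 2 = 660.
- Meeting a Success row: 2 clinical × 2 mycological × 2 antifungal × (3 × 2 + 1) imaging = 56.
- Of these, with a new lesion: 2 × 2 × 2 × 3 = 24.
- With another antifungal needed: 2 × 2 × 7 = 28.
- With both: 2 × 2 × 3 = 12.
- Meeting any progression rule: 24 + 28 − 12 = 40.

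No success combination overlaps through clinical progression, recurrent or emergent disease, or aggregate worsening. These are rule combinations, not patients; they identify the two open routes and say nothing about frequency.

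**3. What does the order do?**

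- *First match wins.* The overlapping patient is a success.
- *Every later rule overrides.* This is unworkable. The Stable row is met by imaging without evidence of progression, so all 24 success combinations with imaging and no new lesion would become Failure-Stable.
- *Failure overrides Success, Stable is only a residual.* The wording permits this, and a new lesion would then mean failure.

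The first is the natural reading of a list tested in sequence. The third cannot be ruled out.

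**4. How wide is the antifungal route?** Several provisions close most of it:

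- Patients withdrawn for an unsuccessful outcome are failures at all later timepoints (SAP 16.1.1).
- Patients withdrawn from study drug, or with an unsuccessful outcome, are not asked back for Day 42 beyond survival status (Protocol Table 1 note b; also Sections 5.1 and 6.3).
- Missing Day 42 response is failure (SAP 16.1.2).
- Patients expected to need antifungal prophylaxis after success should stay on F901318 through Day 42 (Protocol 5.1, 6.3).

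What remains is, for example, an antifungal added while F901318 continues (allowed but discouraged, Protocol 5.9.2.1), if that counts as alternative treatment, or a patient who stopped as a success and began another agent before Day 42.

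**5. Scale.** One reclassified patient is 1/200 = 0.5 points, or 1/100 = 1 point at the initial analysis. As pure illustration, with an assumed 80/200 successes (40.0%, exact 95% CI 33.2 to 47.1):

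| Assumed share of successes overlapping | Rate after correction | 95% CI |
|---|---|---|
| 5% (4 patients) | 76/200 = 38.0% | 31.2 to 45.1 |
| 10% (8 patients) | 72/200 = 36.0% | 29.4 to 43.1 |
| 15% (12 patients) | 68/200 = 34.0% | 27.5 to 41.0 |

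Neither the 40% nor the shares come from the documents.

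**The case against.** The strongest reply is that the outcome is an expert adjudication, not a programmed derivation. The DRC decides it under a Charter that is not among the documents and may bar success when a new lesion is present. That stands as a limit on the practical effect. It does not settle the text, because Protocol 8.2.2 says the SAP will in turn specify the criteria, and the SAP contains no such bar.

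Second, the footnote never says that testing stops once Success is met. This also stands: the rule may be ambiguous rather than plainly wrong. A primary endpoint rule with two workable readings still needs one sentence to choose between them.

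Third, the new-lesion case is narrow. It needs net improvement of at least 25%, clinical resolution, eradication and a lesion without symptoms. Follow-up imaging is directed at the site of disease and otherwise follows local practice (Protocol Table 1 note o), so a silent lesion elsewhere may not be imaged. This limits frequency, not direction.

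A reader might also infer that anyone taken off F901318, switched to another agent and improved at Day 42 is scored a success. The documents do not support that, for the reasons in step 4 of the working.

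**Conclusion.** The concern holds in limited form. Table A's Success and Failure-Progression rows are not mutually exclusive, and read in sequence the footnote scores a patient who meets both as a Day 42 success. Any error is upward only, because the order can move a patient from failure to success but never the reverse. It reaches the secondary overall-response and stable-as-success analyses. The antifungal rule shares the overlap, but only for the small group described above.

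A reader might infer a demonstrated bias of several percentage points. The documents do not support that: they give no rate of new lesions, of added antifungals, or of response. The conclusion rests on the sequential reading and on the Charter containing no overriding rule; if the Charter has one, it and the SAP must be reconciled.

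**What to change.** Change the Table A footnote so that Failure-Progression is tested first, followed by Success-Complete, Success-Partial and Failure-Stable. Alternatively, add to both Success rows that there is no new radiological abnormality attributable to the invasive fungal disease, and no other systemic antifungal needed for the qualifying mould infection.

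Two details matter under either option:

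- The qualifiers are needed. Table A's radiological progression line, unlike its clinical line, is not confined to attributable findings, so an incidental imaging finding would otherwise force failure. Yeast therapy permitted under Protocol 5.9.2.1 should not trigger the antifungal rule.
- The modified-response success row in SAP 16.1.4 needs the exclusion written in. It stands outside the footnote's sequence, accepts any radiological response of 0% or better, and does not mention new lesions.

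Align the DRC Charter, and report how many Day 42 successes also met a progression criterion, so that the effect is visible.

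No new assessments are needed: Protocol 6.3.1.2 already sends main-phase images to central reading and collects the radiology reports. The costs are a response rate that may be slightly lower and, for cases already adjudicated as successes, a check against those reports.
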